#### 15.4.2. Overdose

An overdose is any dose of study treatment given to a subject or taken by a subject that exceeds the dose described in the protocol. Overdoses are not considered AEs and should not be recorded as an AE on the CRF; however, all overdoses must be recorded on an Overdose form and faxed to [REDACTED] within 24 hours of the site becoming aware of the overdose. An overdose must be reported to [REDACTED] even if the overdose does

CONFIDENTIAL

The information contained herein may not be used, disclosed, or published without the written consent of Biogen MA Inc.

not result in an AE. If an overdose results in an AE, the AE must be recorded. If an overdose results in an SAE, both the SAE and Overdose forms must be completed and faxed to [REDACTED]. All study treatment-related dosing information must be recorded on the dosing CRF.

### 15.4.3. Medical Emergency

In a medical emergency requiring immediate attention, study site staff will apply appropriate medical intervention, according to current standards of care. The Investigator (or designee) should contact the [REDACTED] 24-hour emergency medical support number. Refer to the Study Reference Guide's Official Contact List for complete contact information.

#### 15.4.3.1. Unblinding for Medical Emergency

In this study, emergency decoding will be made available to the Investigator and designated personnel at Biogen through IRT.

In a medical emergency when knowledge of the subject's treatment assignment may possibly influence the subject's clinical care, the Investigator may access the subject's treatment assignment by IRT. However, prior to unblinding, the Investigator can contact the [REDACTED] 24-hour emergency medical support number at [REDACTED].

The Investigator must document the reasons for unblinding in the subject's source documents. The Investigator is strongly advised not to divulge the subject's treatment assignment to any individual not directly involved in managing the medical emergency, nor to personnel involved with the analysis and conduct of the study.

## 15.5. Contraception Requirements

For the purposes of this study, women of childbearing potential are defined as all women physiologically capable of becoming pregnant, UNLESS they meet one of the following conditions:

- Postmenopausal
  - 12 months of natural (spontaneous) amenorrhea without an alternative medical cause or 6 weeks after surgical bilateral oophorectomy with or without hysterectomy.
- Post hysterectomy.
- Female surgical sterilization (e.g., bilateral tubal ligation).

For the purposes of this study, highly effective contraception is defined as use of 1 of the following:

- For females of childbearing potential:
  - Established use of oral, injected, or implanted hormonal methods of contraception.

CONFIDENTIAL

The information contained herein may not be used, disclosed, or published without the written consent of Biogen MA Inc.

- Placement of an intrauterine device or intrauterine system
- Barrier methods of contraception with use of a spermicide: condom or occlusive cap (diaphragm or cervical/vault caps) with spermicidal foam/gel/film/cream suppository. The use of barrier contraceptives should always be supplemented with the use of a spermicide.
- Male sexual partners underwent surgical sterilization with the appropriate postvasectomy documentation of the absence of sperm in the ejaculate.
- For males:
  - Vasectomy with negative semen analysis at FU.
  - Use of condoms with spermicide.
  - Female sexual partners who underwent surgical sterilization (e.g., bilateral tubal ligation), are postmenopausal, are post-hysterectomy, or are using highly effective contraception as listed above for female subjects.

For males and females of childbearing potential:

True abstinence, when this is consistent with the preferred and usual lifestyle of the subject, can be considered an acceptable method of contraception based on the evaluation of the Investigator who should also take into consideration the duration of the clinical trial. Periodic abstinence (e.g., calendar, ovulation, symptothermal, postovulation methods) and withdrawal are not considered acceptable methods of contraception.

Pregnancy reporting is described in Section 15.4.1.

## 15.6. Safety Responsibilities

### 15.6.1. The Investigator

The Investigator's responsibilities include the following:

- Monitor and record all AEs, including SAEs, regardless of the severity or relationship to study treatment.
- Determine the seriousness, relationship, and severity of each event.
- Determine the onset and resolution dates of each event.
- Monitor and record all pregnancies and FU on the outcome of the pregnancy in female subjects.
- Complete an SAE form for each SAE and fax it to Biogen SABR (or designee) within 24 hours of the study site staff becoming aware of the event.

CONFIDENTIAL

The information contained herein may not be used, disclosed, or published without the written consent of  
Biogen MA Inc.

- Pursue SAE FU information actively and persistently. FU information must be reported to Biogen SABR (or designee) within 24 hours of the study site staff becoming aware of new information.
- Ensure all AE and SAE reports are supported by documentation in the subjects' medical records.
- Pursue AE FU information, if possible, until the event has resolved or become stable.
- Report SAEs to local EC/IRBs, as required by local law.

#### 15.6.2. Biogen

Biogen's responsibilities include the following:

- Before study site activation and subject enrollment, the Clinical Monitor (██████████) is responsible for reviewing with study site staff the definitions of AE and SAE, as well as the instructions for monitoring, recording, and reporting AEs and SAEs.
- Biogen (or designee) is to notify all appropriate regulatory authorities, central EC/IRBs, and Investigators of SAEs, as required by local law, within required time frames.

CONFIDENTIAL

The information contained herein may not be used, disclosed, or published without the written consent of Biogen MA Inc.

## **16. STATISTICAL METHODS AND DETERMINATION OF SAMPLE SIZE**

The objectives of the study and the endpoints to be analyzed are listed in Section 6.

### **16.1. Demography and Baseline Disease Characteristics**

Demographics and baseline data will be summarized by treatment group with summary statistics (mean, standard deviation [SD], median, and range) or with frequency distributions.

### **16.2. Efficacy and Pharmacodynamics**

#### **16.2.1. Analysis Population**

The intent-to-treat (ITT) population, defined as all subjects who were randomized and received at least 1 dose of study treatment (aducanumab or placebo), will be used for the efficacy analyses. For each endpoint, additional conditions may apply to the definition of the population for the analysis. Subjects will be analyzed in the groups to which they were randomized.

#### **16.2.2. Methods of Analysis**

##### **16.2.2.1. General Considerations**

Summary statistics will be presented. For continuous endpoints, summary statistics will generally include: number of subjects with data, mean, standard deviation, median, and range. For categorical endpoints, this will generally include: number of subjects randomized or dosed, number with data, and the percent of those with data in each category. Statistical testing for efficacy endpoints will be made between each aducanumab regimen and placebo. All statistical tests will be 2-sided.

##### **16.2.2.2. Dose Regimens to be Evaluated**

The following dose regimens of aducanumab as compared with placebo will be evaluated:

- Aducanumab high-dose regimen (6 mg/kg in ApoE  $\epsilon$ 4 carriers and 10 mg/kg in ApoE  $\epsilon$ 4 non carriers).
- Aducanumab 6 mg/kg dose regimen (6 mg/kg in ApoE  $\epsilon$ 4 carriers and ApoE  $\epsilon$ 4 non-carriers).
- Aducanumab low-dose regimen (3 mg/kg in ApoE  $\epsilon$ 4 carriers and 6 mg/kg in ApoE  $\epsilon$ 4 non-carriers).

In the event that the proposed maximum dose (10mg/kg in ApoE  $\epsilon$ 4 non-carriers or 6 mg/kg in ApoE  $\epsilon$ 4 carriers) is terminated after the start of the study (Section 5.3.2) the definition of aducanumab high dose regimen and aducanumab low dose regimen will be modified as shown in Table 12. The dosing modification will be entirely based on interim analysis of outcomes that are independent of, and uninformative about, the treatment-related efficacy effect. Control of

CONFIDENTIAL

The information contained herein may not be used, disclosed, or published without the written consent of Biogen MA Inc.

Type I error rate is thus maintained without a statistical adjustment for such adaptations [Chow and Chang 2011].

**Table 12: Dose Group Pooling Strategy in the Event of Treatment Group Termination**

Treatment group(s) Terminated	Definitions of Revised Pooled Treatment Groups for Comparison
ApoE ε4 carrier high-dose group (6 mg/kg)	Low: ApoE ε4 carrier 3 mg/kg and non-carrier 6 mg/kg High: ApoE ε4 carrier 3 mg/kg and non-carrier 10 mg/kg
ApoE ε4 non-carrier high-dose group (10 mg/kg)	Low: ApoE ε4 carrier 3 mg/kg and non-carrier 6 mg/kg High: ApoE ε4 carrier 6 mg/kg and non-carrier 6 mg/kg
ApoE ε4 carrier high-dose group (6 mg/kg) AND ApoE ε4 non-carrier high-dose group (10 mg/kg)	ApoE ε4 carrier 3 mg/kg and non-carrier 6 mg/kg

### 16.2.2.3. Considerations for Multiple Comparison Adjustments

A sequential (closed) testing procedure will be used to control the overall Type I error rate due to multiple comparisons for the primary endpoint. The order of treatment comparisons is as follows: aducanumab high-dose regimen versus placebo, aducanumab 6 mg/kg regimen versus placebo, and aducanumab low-dose regimen versus placebo. In the event of a dosing modification (see Table 12), the first comparison is the aducanumab high-dose regimen versus placebo and the second comparison is the aducanumab low-dose regimen versus placebo. If the first comparison is statistically significant ( $p \leq 0.05$ ), then the second comparison will also be made at the 0.05  $\alpha$  level. If the second comparison is statistically significant ( $p \leq 0.05$ ), then the third comparison will also be made at the 0.05  $\alpha$  level. However, all comparisons after the initial comparison with  $p > 0.05$  will not be considered statistically significant.

Secondary endpoints have been rank prioritized, in the order shown in Section 6. In order to control for a Type I error for the secondary endpoints, a sequential closed testing procedure will be used and will include both the order of the secondary endpoints and treatment comparisons. Specifically, for each of the secondary endpoints, a sequential (closed) testing procedure, as for the primary endpoint, will be used to control the overall Type I error rate due to multiple treatment comparisons. If statistical significance is not achieved for one, two or all three comparisons, all endpoint(s) of a lower rank will not be considered statistically significant for 1, 2, or all 3 comparisons, respectively.

Due to a current lack of scientific consensus in the AD field on which biomarker(s) might be most appropriate, the selection of the biomarkers and methodology for control of Type I error will be pre-specified in the statistical analysis plan (SAP). Otherwise, there will be no multiple comparison adjustments for the tertiary endpoints.

CONFIDENTIAL

The information contained herein may not be used, disclosed, or published without the written consent of Biogen MA Inc.

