#### **7.4. Study Stopping Rules**

Biogen may terminate this study at any time, after informing Investigators. Biogen (or designee) will notify Investigators when the study is to be placed on hold, completed, or terminated.

Dosing may be terminated by the Sponsor at the recommendation of the IDMC, based exclusively on safety and tolerability data or following the futility analysis, or at the discretion of the Sponsor; therefore there are no study-specific stopping rules defined in this protocol.

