### **16.6.2. Interim Superiority Analysis**

An interim analysis for superiority may be performed after approximately 50% of the subjects have completed the Week 78 Visit (or discontinued). The Lan-DeMets method with O'Brien-Fleming stopping boundary for efficacy will be used. In order to maintain the treatment blind in the event of this interim analysis, an independent group external to Biogen that will not be involved in the conduct of the study after unblinding will perform the interim superiority analysis. The independent group will present the unblinded interim analysis to the IDMC. The aim of this interim analysis is to allow the possibility to demonstrate treatment effect early. The analysis will be discussed in detail in the SAP.

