### **16.7. Sample Size Considerations**

The study's sample size is based, in part, on results from a protocol-specified interim analysis from Study 221AD103 which included 1 year data from 1, 3 and 10 mg/kg treatment groups.

A sample size of 450 subjects per treatment group will have approximately 90% power to detect a true mean difference of 0.5 in change from baseline CDR-SB at Week 78 between the 2 treatment groups. This power calculation is based on a 2-sided t-test assuming equal variance with a final significance level of 0.05, a SD of 1.92 and a drop-out rate of 30%. The SD estimate of 1.92 for Week 78 reflects a 39% increase over the SD from the protocol-specified interim analysis of 1-year data.

The assumed true mean difference of 0.5 between the 2 treatment groups represents an approximately 25% reduction in the placebo mean change from baseline at Week 78 if the placebo mean change is estimated to be 2.

The sample size may be reassessed in a blinded manner approximately 3 months before enrollment is complete if at least 15% of the data are available on the primary endpoint. At this interim time-point, the SD for the primary endpoint will be estimated based on the blinded data. The sample size may be increased if the SD is estimated to be more than approximately 2.07. In addition, the sample size could be increased using external clinical trial results that become available after the start of the study.

CONFIDENTIAL

The information contained herein may not be used, disclosed, or published without the written consent of Biogen MA Inc.

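### Protocol v3.0 keeps a final significance level of 0.05 for every comparison while permitting an O'Brien-Fleming efficacy look at about 50%; if the look is taken, the final level should be about 0.0490

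*Protocol*

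**What the plan says.** All references are to protocol v3.0 unless stated.

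- **Section 16.6.2** makes the efficacy look optional: "An interim analysis for superiority may be performed after approximately 50% of the subjects" have completed Week 78 or discontinued. For the boundary it says: "The Lan-DeMets method with O'Brien-Fleming stopping boundary for efficacy will be used". Detail is left to the SAP.
- **Section 16.2.2.3** sets a fixed testing order of high dose, 6 mg/kg regimen, low dose, each against placebo. The gate is p ≤ 0.05. Once the first comparison passes, "then the second comparison will also be made at the 0.05" level; once the second passes, "then the third comparison will also be made at the 0.05" level. No interim look is mentioned.
- **Section 16.7** claims: "A sample size of 450 subjects per treatment group will have approximately 90% power to detect a true mean difference of 0.5", computed for a two-sided t-test "with a final significance level of 0.05, a SD of 1.92 and a drop-out rate of 30" per cent.
- **Section 7.4** names safety and tolerability, the futility analysis and Sponsor discretion as grounds for ending dosing, and concludes: "therefore there are no study-specific stopping rules defined in this protocol".

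The 0.05 wording in Sections 16.2.2.3 and 16.7 is the same in v1.0, v2.0 and v3.0. In v1.0 the superiority look was planned outright; from v2.0 it is optional.

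**The concern.** A Lan-DeMets design shares the 0.05 between the looks. Whatever is spent at the interim is no longer available at the end, so the final critical value has to be stricter than 1.96. Sections 16.2.2.3 and 16.7 state the threshold of a design with a single analysis. In v1.0, where the look was firmly planned, the same 0.05 already stood beside it, so the figure was not written for a trial without an interim.

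At stake is the primary decision rule. If the look is taken and the final p-value falls between 0.0490 and 0.05, the trial is positive under Section 16.2.2.3 and negative under the method named in Section 16.6.2. An SAP that uses the reduced level would contradict the protocol; an SAP that follows the protocol would overspend.

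**Working it through.** **Inputs.** Overall two-sided level 0.05 and p ≤ 0.05 per comparison (16.2.2.3); look at about 50% (16.6.2); 450 per group, difference 0.5, SD 1.92, drop-out 30%, final level 0.05 (16.7).

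**1. Reproduce the stated power.** Evaluable per arm: 450 × (1 − 0.30) = 315. With a two-sided 0.05, power is 90.5% by the normal approximation and 90.4% by the noncentral t. In reverse, 310 evaluable per arm are needed for 90%, and 310 / 0.70 gives 443 per arm against the 450 planned. The stated figure therefore reproduces at an unadjusted final 0.05, with nothing set aside for an interim.

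**2. Interim spend at information fraction t = 0.5.** With 0.025 in each tail, the O'Brien-Fleming-type function spends 2 × [1 − Φ(2.2414/√t)] per tail. Over both tails:

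2 × 2 × [1 − Φ(2.2414/√0.5)] = 0.00305, that is |Z| ≥ 2.963.

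**3. Overall error if 0.05 is kept at the end.** The interim and final statistics are bivariate normal with correlation √0.5 under the null:

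P(|Z₁| ≥ 2.963 or |Z₂| ≥ 1.960) = 0.0510.

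**4. Final level that restores 0.05.** Solving P(|Z₁| ≥ 2.963 or |Z₂| ≥ c) = 0.05 gives c = 1.969, a nominal two-sided p of 0.0490.

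**5. Sensitivity to the information fraction.** Half of the subjects completing or discontinuing need not be exactly half of the information.

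| Fraction | Interim level | Overall error with final 0.05 | Final level needed |
|---|---|---|---|
| 40% | 0.0008 | 0.0503 | 0.0497 |
| 50% | 0.0031 | 0.0510 | 0.0490 |
| 60% | 0.0076 | 0.0523 | 0.0476 |

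**6. Power after correction.** At a final level of 0.0490, t-test power is 90.2%, against 90.4% at 0.05. The number needed for 90% is 312 evaluable, and 312 / 0.70 gives 446 per arm, still below 450. At the level for a 60% look (0.0476) it is 449 per arm.

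**The case against.** The best defence is that naming the spending function already fixes both boundaries, that Section 16.2.2.3 is about multiplicity across regimens and not across looks, that the 0.05 in Section 16.7 is only a power assumption, and that numerical boundaries commonly sit in the SAP. Much of this is fair, and the absence of boundary values from the protocol is no fault. What remains is that the protocol does state a number for significance and a number for the final level, and both are wrong if the look is taken. Deferring detail to the SAP does not change what the protocol itself fixes.

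The defence also notes that the text examined is v3.0. The v4.0 table of contents still lists Sections 16.2.2.3 and 16.6.2, but their text is not supplied. The v4.0 synopsis gives carriers 3 or 10 mg/kg, so the 6 mg/kg regimen, and with it the three-step sequence, probably did not survive unchanged. That limits the point to the text available.

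Three stronger readings are tempting, and the documents do not support them:

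- *Later comparisons are tested at 0.05 at both looks, with a much larger error.* This needs 0.05 to apply at the interim, where Section 16.6.2 prescribes the O'Brien-Fleming boundary, and it needs the trial to continue after crossing what that section calls a stopping boundary.
- *The decision to spend alpha is made after the futility results are seen.* The futility and superiority looks share a time point and the same committee, but Section 16.6.2 does not say who decides or when. Nothing places the decision after unblinding.
- *Section 7.4 rules out an efficacy stop.* It lists Sponsor discretion, which could cover one. The conflict is one of wording: no stopping rules on one page, a named stopping boundary on another.

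**Conclusion.** The point holds as a minor but real error. In v3.0, and in the identical 0.05 wording of v1.0 and v2.0, taking the superiority look at 50% and then testing at 0.05 gives the first comparison a two-sided type I error of 0.0510, an excess of about 0.1 percentage point. The level consistent with the named method is 0.0490. The sample size and the claim of about 90% power are not affected.

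This rests on the look being taken, since without it 0.05 is correct; on information close to 50%; on the usual bivariate normal approximation; and on giving no credit for a futility stop, which Section 16.6.1 frames as something the IDMC may recommend. It alters a conclusion only for a final p-value between 0.0490 and 0.05.

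**What to change.** - In Sections 16.2.2.3 and 16.7, state that when the superiority look is taken, every comparison in the sequence is tested at the spending-function level for that look: 0.00305 at the interim and 0.0490 at the end for exactly 50% information, both recomputed at the observed fraction. State that 0.05 applies only when the look is not taken.
- In Section 16.6.2, state that whether the look takes place is decided and documented before any unblinded efficacy data are reviewed.
- Reconcile the statement in Section 7.4 that no stopping rules are defined with the efficacy stopping boundary named in Section 16.6.2.
- Check whether Section 16 of v4.0 carries the same wording and correct it there as well.

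The cost is protocol wording, with matching SAP text. The final threshold moves from 0.050 to 0.0490 if the look is taken, power goes from 90.4% to 90.2%, and 450 per group stands.

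### The secondary-endpoint gate blocks only the regimen that failed, so family-wise error across the secondary endpoints and regimens is not held at 5% as Section 16.2.2.3 claims

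*Protocol*

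**What the plan says.** All of this is in Protocol Section 16.2.2.3, version 3.0. Versions 1.0 and 2.0 carry essentially the same text.

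- **Order of regimens:** "aducanumab high-dose regimen versus placebo, aducanumab 6 mg/kg regimen versus placebo, and aducanumab low-dose regimen versus placebo". After a dosing modification there are only two: "the first comparison is the aducanumab high-dose regimen versus placebo and the second comparison is the aducanumab low-dose regimen versus placebo".
- **Alpha:** each success passes the full level on ("then the second comparison will also be made at the 0.05" level), and Section 16.2.2.1 adds "All statistical tests will be 2-sided".
- **Order of endpoints:** "Secondary endpoints have been rank prioritized, in the order shown in Section 6". Section 6.2 lists MMSE, then ADAS-Cog 13, then ADCS-ADL-MCI.
- **Aim:** "In order to control for a Type I error for the secondary endpoints, a sequential closed testing procedure will be used", and this procedure "will be used and will include both the order of the secondary endpoints and treatment comparisons". Within each secondary endpoint the regimens follow the same sequence as for CDR-SB.
- **Gate between endpoints:** if one, two or all three comparisons fail, "all endpoint(s) of a lower rank will not be considered statistically significant for 1, 2, or all 3 comparisons, respectively".

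The section leaves to the SAP only the choice of biomarkers and their error control. The secondary-endpoint rule is fixed in the protocol.

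**The concern.** The last sentence makes the gate specific to each comparison. Suppose high dose is significant on MMSE and low dose is not. Low dose is then barred from ADAS-Cog 13, but high dose goes on to it at 0.05. The sequence has split into two branches, and each carries the full 0.05. That is neither a single fixed sequence nor a closed test.

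The protocol defines the secondary family as endpoints by regimens and says Type I error is controlled over both. If two or three true null hypotheses in that family can be open at 0.05 at once, the stated control fails. A set of secondary claims would then carry more than the 5% joint error a reader of the protocol would assume. An SAP that follows the protocol would inherit the problem, and it cannot credibly be repaired after unblinding.

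**Working it through.** **Inputs from the protocol (version 3.0).** Two-sided 0.05 per test; regimen and endpoint orders as above; 1:1:1 allocation and 60% to 70% ApoE ε4 carriers (Section 7.1); 450 per group, difference 0.5, SD 1.92, 30% drop-out, about 90% power (Section 16.7).

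**Assumption.** The protocol gives no correlation between endpoints. The range 0.3 to 0.7 is used.

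**1. The protocol's own figures.** Evaluable per group: 450 × 0.7 = 315. The noncentrality is 0.5 / (1.92 × √(2/315)) = 3.27, so power by the noncentral t is 90.4%, as stated. The regimen sequence on CDR-SB alone has simulated family-wise error of 5.0%.

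**2. Two regimens, by hand.** Let high dose truly work on MMSE and every other secondary hypothesis be null. Once high dose passes MMSE, two true nulls are open at 0.05: low dose on MMSE and high dose on ADAS-Cog 13. If they were independent, the error would be 1 − 0.95² = 9.75%. The shared placebo group correlates the high- and low-dose contrasts at 0.5, so these two statistics correlate at 0.5 × the endpoint correlation. For endpoint correlations 0.3, 0.5 and 0.7 the bivariate normal gives 9.7%, 9.6% and 9.4%.

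**3. Three regimens, by hand.** Low dose on MMSE, 6 mg/kg on ADAS-Cog 13 and high dose on ADCS-ADL-MCI can all be open together. If they were independent, the error would be 1 − 0.95³ = 14.3%.

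**4. Simulation of the rule, secondary family only.** There were 1,000,000 trials per cell and 65% carriers. A regimen is rejected on an endpoint only if p ≤ 0.05, the preceding regimen was rejected on that endpoint, and the same regimen was rejected on the preceding endpoint. In the planned-effect rows, each non-null comparison has the noncentrality of 3.27 from step 1; applying it to the secondary endpoints is itself an assumption.

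| Configuration | r = 0.3 | r = 0.5 | r = 0.7 |
|---|---|---|---|
| Two regimens, gate passed almost surely | 9.7% | 9.6% | 9.4% |
| Two regimens, gate at planned effect | 8.0% | 7.6% | 6.9% |
| Three regimens, all gates passed almost surely | 13.9% | 13.4% | 12.7% |
| Three regimens, gates at planned effect | 9.3% | 8.7% | 7.7% |

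Under the global null the rule gives 5.0%.

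**5. A single chain instead.** All regimens are tested on MMSE, then all on ADAS-Cog 13, then all on ADCS-ADL-MCI, and the first failure stops everything after it. Simulated error in the same worst-case configurations is 5.0% for two and for three regimens.

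**The case against.** **It could be meant as one chain.** That reading would control error at 5%, but the words one, two or all three, respectively, would then have no function. At the least the sentence needs replacing.

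**The figures are worst cases.** True, and that is how strong control is judged. The two-regimen trigger is also ordinary: high dose works on an endpoint and low dose does not. The three-regimen maximum is different. It needs 6 mg/kg to be null on an endpoint where high dose is almost sure to succeed, yet in version 3.0 these two regimens share all their carriers. Without opposite effects in the subgroups, the whole high-dose effect must come from non-carriers. At 35% non-carriers, 90% power then needs 0.26 / 0.35 = 0.74 SD in that subgroup, against a planned 0.5 / 1.92 = 0.26 SD. A reader might take 13% to 14% as the expected error, and the design does not support that.

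**CDR-SB.** A reader might infer that joint 5% control over CDR-SB and the secondary endpoints is claimed and broken. Section 16.2.2.3 claims control for the primary endpoint and, separately, for the secondary endpoints. It states no joint level, so only the secondary-family figures bear on its claim.

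**Version.** This stands as a limit. The version 4.0 synopsis gives carriers 10 mg/kg in the high-dose group, so the pooled 6 mg/kg regimen no longer has a carrier group and the three-regimen set may be gone. Section 16 of version 4.0 is not in the text at hand. A two-regimen set under the same wording would still have the problem.

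**Conclusion.** The claim of Type I error control for the secondary endpoints is wrong as worded in version 3.0. Over the secondary endpoints and regimens taken together, family-wise error reaches about 9.4% to 9.7% with two regimens, or about 7% to 8% when the gate is passed at planned-effect power. With the version 3.0 three-regimen set it reaches about 13% to 14% only in the extreme configuration, and about 8% to 9% at planned-size effects. These figures rest on the assumed endpoint correlations of 0.3 to 0.7. At 0.9 the worst cases fall to about 9.2% and 11.6%, still well above 5%.

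A reader might go further and say that secondary claims under this rule have no confirmatory value. The documents do not support that. Error is held at 5% within one endpoint across regimens and within one regimen across endpoints. Where every regimen succeeds on the earlier endpoints, the rule gives the same claims as a single chain. The CDR-SB regimen sequence is unaffected. What fails is the joint control that the section asserts.

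**What to change.** Replace the last sentence of the secondary-endpoint paragraph with one of these:

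1. **A single fixed sequence over the secondary family.** If any regimen comparison on a secondary endpoint is not significant, no regimen is declared significant on any lower-ranked secondary endpoint.
2. **A graphical procedure that splits alpha among the secondary hypotheses only** and leaves the CDR-SB regimen sequence at 0.05. The restriction matters: if the split extended to CDR-SB and the next regimen were tested there at 0.025, its power at the planned effect would fall from 90.4% to 84.6% until alpha was recycled.
3. **If neither is wanted, a narrower claim:** error is controlled within each regimen across endpoints and within each endpoint across regimens, but not jointly.

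The change is to wording in the protocol, carried into the SAP. The statistical cost of options 1 and 2 is that high-dose claims on lower-ranked secondary endpoints are lost, or tested at a smaller alpha, when a lower regimen fails. The CDR-SB tests keep their level. Check Section 16.2.2.3 of version 4.0 for the same sentence, and for how many regimens it still compares, before amending.
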